8.1 Adverse events (AE)

An adverse event (AE) is defined as any untoward medical occurrence in a patient or clinical investigation subject who has received radiation therapy for MCSS. This does not necessarily have a causal relationship with the treatment. An AE can therefore be any unfavourable and unintended symptom, (including an abnormal laboratory finding), or disease temporarily without any association with radiation therapy for MCSS. The AEs that will be reported are based upon organs at risks that most likely will be affected from radiation therapy for MCSS.

All adverse events will be graded according to the PRO-CTCAE scale and will be reported on the appropriate CRF-form.

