4.2 Toxicity assessment

All toxicity assessment will be patient reported. If the patient cannot access the internet formula, the local investigator or a substitute will call them on the phone and record answers to the questions. QoL of Life schemes will be sent by mail. We will use the PRO symptom assessment that is found most suitable from an "pilot assessment" of different questions assessing oesophageal pain, difficulty swallowing, heart burn, nausea, pain from the irradiated volume and changes in pain medication. PRO symptoms will be daily assessed from start of radiotherapy and five weeks ahead,

from week 6-9 PRO symptoms will be assessed weekly. The participants will be reminded through a text message to their mobile phone or an email with a direct link to the eCRF in REDCap.

Patients participating in Flash glucose monitoring will be informed of symptoms of hyperglycaemia including needing to pee frequently, tiredness, recurrent infections and bad wound healing. See appendix E. Patients will be thoroughly instructed to contact the PI if symptoms of hyperglycaemia should occur. As many of the symptoms of hyperglycaemia overlap with symptoms related to end stage cancer, commencement of glucose measurements will be based on an individual assessment. If hospitalization is deemed necessary, glucose measurements will be at the discretion of the treating physician. If the patient is hospitalized for any reason, glucose measurements and treatment of hyperglycaemia if present, will be at the discretion of the treating physician.

The PRO questionnaire will contain a field where other symptoms not related to esophagitis can be recorded. See appendix A. If complete, this will appear as a pop-up message with the PI. Symptoms will then be assessed for symptoms of hyperglycaemia.

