8.2 Serious adverse events

A serious adverse event (SAE) in human trials is defined as any untoward medical occurrence that, at any dose, results in death or is life-threatening, is disabling, requires hospitalization (whether initial or prolonged and does not include planned hospitalization) or requires intervention to prevent permanent impairment/damage. In ESO-SPARE SAEs are only registered within the nine weeks study period unless the SAE started within the 9 weeks study period but is not settled after the expiration

of the nine-weeks study period. All SAEs must be registered by the local investigator on the appropriate CRF and must be followed until they are fully settled.

Progression or deteriorating of malignancy during the study (including new metastatic lesions or death due to progression), will be part of the efficacy assessment and should NOT be reported as an AE/SAE. Symptoms clearly associated with malignancy or with concomitant or sequential systemic treatment, e.g. chemotherapy, during the study should NOT be reported as AE / SAE unless they are:

- Newly emerged (i.e. not present at baseline) and correlation with the underlying malignancy or systemic treatments are unclear.
- If there is any uncertainty as to whether an exacerbation of the subject's condition is due to the cancer disease or due to an AE, it must be reported as an AE or an SAE depending on the situation.

The local Investigator (together with the treating physician) must determine the relationship between the radiation treatment and the occurrence of a SAE as not suspected or suspected as defined below:

Not suspected:	A causal relationship of the radiation treatment is unlikely or remote, or other medications, therapeutic interventions, or underlying conditions provide enough explanation for the observed event.
Suspected:	There is a reasonable possibility that the radiation treatment caused the adverse event. 'Reasonable possibility' means there is evidence to suggest a causal relationship between the radiation treatment and the adverse event.

Furthermore, the local investigator (together with the treating physician) must determine whether a suspected serious adverse event is expected, or unexpected as defined below:

Expected:	If the treating physician/local investigator recognize the suspected SAE as an event reported in the literature and/or known from the clinical experience, this adverse event should be considered as expected.

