Unexpected:	If the treating physician/local investigator do not recognize the suspected SAE as an event reported in the literature and/or known from the clinical experience, this event should be considered as unexpected.

The assessment of an SAE should be based upon organs at risks that most likely will be affected from the radiation. Any suspected, unexpected SAE must be reported by the local investigator to the sponsor within one working day (after being aware of the incident). The sponsor can choose to change the registration of a suspected unexpected SAE to a suspected expected SAE after an audit of the case. The sponsor will inform the Ethical Committees of all relevant information about unexpected SAE, suspected to be related to the radiation treatment, that are fatal or life-threatening as soon as possible, and in any case no later than seven days after knowledge of such a case. Relevant follow-up information for these cases will subsequently be submitted within an additional eight days.

Once a year throughout the clinical trial, the sponsor will provide an updated safety report highlighting SAE to the Ethics Committee. For events not reported in the CTCAE version 5.0, the investigator will use the grade or adjectives reported in the following:

Grade 1 Mild does not interfere with patient's usual function

Grade 2 Moderate Interferes to some extent with patient's usual function

Grade 3 Severe, Interferes significantly with patient's usual function

Grade 4 Life-threatening, results in a threat to life or in an incapacitating disability

Grade 5 Death

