8.3 Trial management committee (TMC)

A trial management committee (TMC) is set up with the participation of representatives from the different centers and specialist (radiation oncologist and medical physicist). The TMC will meet annually after study initiation. All events (See primary endpoint), will be reviewed by the TMC and if the rate of reirradiation at one year is excessive defined by the sample size calculation, then the TMC can, at its discretion recommend cessation of the study or dose adjustment. Furthermore, all grade 4 and 5 toxicity deemed caused by the radiation treatment will be reviewed by the TMC.

9 Ethical aspects

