Table 2: Distribution of ambulatory function. The conventional arm follows the SCORAD trial (Hoskin et al., 2019).

Recruitment, withdrawal, and follow-up

Enrollment, intervention, allocation, follow-up, and data analysis will be summarized in a CONSORT diagram in accordance with CONSORT 2010 guidelines (4)

Statistical principles

Confidence intervals and P values

Level of significance: $p < 0.05$ with no adjustment for multiplicity. Confidence intervals are reported at 95 % limits (bound by zero) and calculated by the binominal distribution for rates and as per Kaplan-Meier method for time-to-event analyses.

Analysis

We will report our data in accordance with the CONSORT 2010 guidelines including the CONSORT Patient-Reported Outcome (PRO) extension (4,5) .

Analyses will be performed per-protocol for all patients who have received any study treatment.

Primary analysis of NCI-PRO-CTC-AE toxicity will only include weeks where ≥ 3 days questionnaires are completed.

Primary analysis of EQ-5D-5L and EORTC-QLQ-C30 will only include completed questionnaires.

All CTC-AE and PRO-CTC-AE grades will be reported.

Missing data will be described in detail, see missing data section.

A. Co-primary endpoints

1. Peak dysphagia (difficulty swallowing) measured by NCI-PRO-CTC-AE within 5 weeks after start of radiotherapy (daily measurements).

PRO-CTC-AE responses are scored from 0 to 4, with 0 representing "None" and 4 representing "Very severe". For each patient the peak value within 5 weeks after start of radiotherapy (daily measurements) will be included in the analysis. Difference in scores between treatment arms will be compared using Wilcoxon rank-sum test.

2. Ambulatory function measured by EQ-5D-5L mobility dimension at 9 weeks after start of radiotherapy.

EQ-5D-5L measures individual generic health status using 5 dimensions: mobility, self-care, usual activities, pain/discomfort, and anxiety/depression. Each dimension has 5 levels depending on the severity of symptoms, with 1 representing “No problems” and 5 representing “Extreme problems”. Difference in scores between mobility dimension treatment arms will be compared using Wilcoxon rank-sum test.

B. Severity of dysphagia, nausea and dyspepsia measured by NCI-PRO-CTC-AE [Time Frame: Week 1-9 after start of radiotherapy (repeated measurement)].

CTC-AE responses are scored from 0 to 4, with 0 representing “None” and 4 representing “Very severe”.

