For each of the first five weeks, where daily measurements are recorded, the peak value will be used for analysis. Changes in severity score over time (repeated measurement) will be analyzed using Generalized Linear Mixed Models.

C. Duration of dysphagia, nausea and dyspepsia measured by NCI-PRO-CTC-AE [Time Frame: within five weeks after start of RT (daily measurements) and at 6, 7, 8, and 9 weeks].

Duration of toxicity will be presented graphically in separate figures.

For the first five weeks mean duration (days) in each group will be compared using Wilcoxon rank-sum test.

D. Severity of cough, oropharyngeal pain, dyspnea, dysphagia, hoarseness, and dyspepsia measured by CTC-AE (weekly measurements) [Time Frame: Week 1-5 after start of radiotherapy (repeated measurement)].

CTC-AE responses are scored from 0 to 4, with 0 representing “None” and 4 representing “Very severe”.

Changes in severity score over time (repeated measurement) will be analyzed using Generalized Linear Mixed Models.

E. Duration of cough, oropharyngeal pain, dyspnea, dysphagia, hoarseness, and dyspepsia measured by CTC-AE (weekly measurements) [Time Frame: Week 1-5 after start of radiotherapy (repeated measurement)].

Duration of toxicity will be presented graphically in separate figures. Mean duration (weeks) in each group will be compared using Wilcoxon rank-sum test.

F. Demographics: Subject demographics, baseline characteristics and medical history will be summarized descriptively. Generally, range, mean and standard deviation, or median and inter quartile range, will be reported for continuous variables. Frequencies and proportions will be reported for categorical variables.

G. Treatment site pain response [Time frame: weekly, 1-9 weeks after start of RT]:

Only patients with baseline pain will be included in the analysis.

Pain response will be measured by the ICPRE score (6). Possible responses are “Complete response”, “Partial response”, “Pain Progression” and “Intermediate response”.

For each of the first five weeks, where daily measurements are recorded, the worst response will be used for analysis. Changes in ICPRE score over time (repeated measurement) will be analyzed using Generalized Linear Mixed Models.

H. Duration of treatment site pain response [Time Frame: Weekly week 1-9 after start of radiotherapy].

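### The protocol names conflicting scales for grading adverse events, SAP item D puts patient-reported labels on CTC-AE items, and the rule for an expected SAE has no severity limit

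*Protocol*

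**What the plan says.** **Grading.** Protocol section 8.1: "All adverse events will be graded according to the PRO-CTCAE scale". Section 4.2 adds: "All toxicity assessment will be patient reported". The SAP, under the first co-primary endpoint, gives the range: "PRO-CTC-AE responses are scored from 0 to 4", from *None* to *Very severe*. Appendix A shows the same five levels, with *Almost constantly* as the top level of the frequency items.

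Section 8.2 works differently. It defines an SAE by its outcome (death, threat to life, disability, hospitalisation, or intervention to prevent permanent damage) and has the local investigator register it on the CRF. On grades it says: "For events not reported in the CTCAE version 5.0, the investigator will use the grade or adjectives reported in the following". The list that follows runs from 1 to 5, where 4 is life-threatening and 5 is death.

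**Committee trigger.** Section 8.3: "all grade 4 and 5 toxicity deemed caused by the radiation treatment will be reviewed by the TMC". No scale is named.

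**SAP item D.** Six symptoms, listed among the SAP's secondary endpoints as CTC-AE version 5 and registered from patient no. 107, are to be analysed under this rule: "CTC-AE responses are scored from 0 to 4", again from *None* to *Very severe*.

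**Expectedness.** Section 8.2 lets the treating physician or local investigator decide. If they recognise a suspected SAE as an "event reported in the literature and/or known from the clinical experience, this adverse event should be considered as expected". Rapid reporting covers only the rest: "Any suspected, unexpected SAE must be reported by the local investigator to the sponsor within one working day". The sponsor's seven-day report to the ethics committees is for unexpected, suspected SAEs that are fatal or life-threatening. The sponsor may move an event from unexpected to expected after an audit; no move in the other direction is described. An annual safety report covers SAEs generally.

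**The concern.** Section 1.2 of the protocol says that sparing the esophagus may raise the dose to other organs and names the lungs. Serious toxicity in the experimental arm therefore needs a clear path to the people who can act on it. Two of the protocol's paths are a grade trigger for the TMC and an unexpectedness trigger for rapid reports. The first does not say which of two incompatible scales it uses. The second can be switched off for an event of any severity once its type is known. The SAP table and model for the CTC-AE items would also carry the wrong labels, so a reader could take a grade 4 there for a strong symptom when section 8.2 means a threat to life.

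**Working it through.** No figure in the plan bears on this point and no arithmetic decides it. The check is a comparison of the passages, followed by applying them to cases.

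**Step 1. The scales side by side.**

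| Place | Scale | Meaning of 4 | Meaning of 5 |
|---|---|---|---|
| Protocol 8.1, with Appendix A and the SAP scoring rule | PRO-CTCAE, 0 to 4 | *Very severe* (or *Almost constantly*) | none |
| Protocol 8.2 | CTCAE v5.0 implied; own list 1 to 5 for events outside it | life-threatening (own list) | death (own list) |
| Protocol 8.3 | not named | not stated | not stated |
| SAP item D | CTC-AE v5, scored 0 to 4 | *Very severe* | none |

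Section 8.3 speaks of a grade 5, which exists only on the section 8.2 side. Section 8.1 nevertheless covers all adverse events. The two can be reconciled only by assuming that 8.1 does not mean what it says.

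**Step 2. How far section 8.2 fills the gap.** Its list applies only to events outside CTCAE v5.0. No protocol sentence says that events inside CTCAE v5.0 are graded by it; that is implied. The SAP itself treats cough, dyspnea, dysphagia and hoarseness as CTC-AE version 5 items, so the list does not cover them. For these symptoms the only explicit scoring rules are section 8.1 and SAP item D, and both stop at 4.

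**Step 3. Scope of item D.** With the planned 200 patients and consecutive numbering, registration from patient no. 107 covers at most 200 − 107 + 1 = 94 patients. Within that group the label for 4 differs from section 8.2, and a grade 5 has no score.

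**Step 4. The reporting rules applied to cases.** Each case is an SAE suspected to be due to radiation.

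- *Fatal, type not recognised.* Unexpected, so both the one-working-day and the seven-day reports apply. The rule works, and no grade is needed.
- *Fatal or life-threatening, type recognised.* Expected under the literal rule, so neither report applies. The stated routes left are registration on the CRF, the annual safety report, and TMC review if the event is graded 4 or 5 on the section 8.2 meaning.
- *Severe but neither fatal nor life-threatening, type recognised.* Expected, so there is no one-working-day report. The seven-day report would not have applied in any case.

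**Step 5. Whether the second case is realistic.** Section 9.2 cites earlier trials with grade 3 esophagitis in 1.5% of patients, and with grade 3-4 events in about 20.5%, dominated by fatigue, pain and respiratory symptoms. Esophageal and respiratory injury are therefore recognised types on the protocol's own account. Nothing in section 8.2 separates a fatal form from the form described.

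**The case against.** A reader might infer that the two triggers cannot work at all. The documents do not support that. SAEs are defined by outcome and registered by the investigator, and both rapid reports turn on seriousness, causality and unexpectedness, so the choice of scale does not touch them. An unrecognised event still triggers them. Section 8.2 does supply grades 4 and 5, and since a grade 5 exists only there, the natural reading of section 8.3 is the CTCAE meaning. TMC review also requires that the toxicity be judged radiation-related, so one patient tick of *Very severe* heartburn is not evidently meant to reach the committee. A life-threatening lung event belongs on the SAE form, not on the patient questionnaire.

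Two examples that come to mind are weak. Radiation myelopathy is described in section 9.2.1 as late, while SAEs are registered within nine weeks. Grade 3 esophagitis is neither fatal nor life-threatening, so it says nothing about the seven-day report.

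A delay of about twelve months might be inferred from the annual report and the annual TMC meeting. That is at most an upper bound. The protocol sets no interval for expected SAEs to reach the sponsor, the CRF is electronic, the sponsor has access to patient records, and section 8.3 does not say that review of grade 4 and 5 toxicity waits for the meeting.

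On item D, the SAP does not say who grades, and whether each of the six symptoms can reach grade 5 depends on CTCAE v5.0, which is not among the documents.

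All of this limits the point. It does not remove the conflict between 8.1 and 8.2, the unnamed scale in 8.3, the wrong anchors in item D, or the missing severity limit.

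**Conclusion.** Three faults stand, and they should be corrected.

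1. Sections 8.1 and 8.2 name different scales and section 8.3 names none. The TMC trigger is ambiguous, though it can be read sensibly.
2. SAP item D gives CTC-AE version 5 items the PRO-CTCAE anchors, so grade 4 is mislabelled and grade 5 has no score, for at most 94 of 200 planned patients.
3. The expectedness rule has no severity limit, so a suspected fatal or life-threatening event of a known type can miss both rapid reports. This is the most serious of the three.

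The third conclusion rests on reading the rule literally; a cautious investigator might report such an event anyway, but the text does not require it. The documents give no SAE counts, so the number of reports affected cannot be estimated.

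**What to change.** **Protocol 8.1 to 8.3.** Grade investigator-recorded AEs and SAEs on CTCAE version 5.0, with the section 8.2 list for events outside it. Keep PRO-CTCAE for the patient-reported endpoints. State in 8.3 that its trigger uses the CTCAE grade.

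**SAP item D.** Replace the *None* to *Very severe* anchors with the CTCAE version 5.0 grades.

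**Protocol 8.2, expectedness.** Treat a suspected SAE as unexpected when its severity or outcome exceeds what is described for that event type. A suspected fatal or life-threatening SAE not documented at that severity then goes through the one-working-day and seven-day reports. Section 9.2 is narrative and cannot serve as the reference as it stands, so a short written list of event types with their described severities is needed.

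**Cost.** Wording, one list, and a few more expedited reports; SAEs are already on a CRF. The SAP puts last inclusion no later than 30 April 2024. If accrual has closed, correcting item D and grading the registered SAEs on the one named scale can still be done before reporting.

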8.2 Serious adverse events

A serious adverse event (SAE) in human trials is defined as any untoward medical occurrence that, at any dose, results in death or is life-threatening, is disabling, requires hospitalization (whether initial or prolonged and does not include planned hospitalization) or requires intervention to prevent permanent impairment/damage. In ESO-SPARE SAEs are only registered within the nine weeks study period unless the SAE started within the 9 weeks study period but is not settled after the expiration

of the nine-weeks study period. All SAEs must be registered by the local investigator on the appropriate CRF and must be followed until they are fully settled.

Progression or deteriorating of malignancy during the study (including new metastatic lesions or death due to progression), will be part of the efficacy assessment and should NOT be reported as an AE/SAE. Symptoms clearly associated with malignancy or with concomitant or sequential systemic treatment, e.g. chemotherapy, during the study should NOT be reported as AE / SAE unless they are:

- Newly emerged (i.e. not present at baseline) and correlation with the underlying malignancy or systemic treatments are unclear.
- If there is any uncertainty as to whether an exacerbation of the subject's condition is due to the cancer disease or due to an AE, it must be reported as an AE or an SAE depending on the situation.

The local Investigator (together with the treating physician) must determine the relationship between the radiation treatment and the occurrence of a SAE as not suspected or suspected as defined below:

Not suspected:	A causal relationship of the radiation treatment is unlikely or remote, or other medications, therapeutic interventions, or underlying conditions provide enough explanation for the observed event.
Suspected:	There is a reasonable possibility that the radiation treatment caused the adverse event. 'Reasonable possibility' means there is evidence to suggest a causal relationship between the radiation treatment and the adverse event.

Furthermore, the local investigator (together with the treating physician) must determine whether a suspected serious adverse event is expected, or unexpected as defined below:

Expected:	If the treating physician/local investigator recognize the suspected SAE as an event reported in the literature and/or known from the clinical experience, this adverse event should be considered as expected.
Unexpected:	If the treating physician/local investigator do not recognize the suspected SAE as an event reported in the literature and/or known from the clinical experience, this event should be considered as unexpected.

The assessment of an SAE should be based upon organs at risks that most likely will be affected from the radiation. Any suspected, unexpected SAE must be reported by the local investigator to the sponsor within one working day (after being aware of the incident). The sponsor can choose to change the registration of a suspected unexpected SAE to a suspected expected SAE after an audit of the case. The sponsor will inform the Ethical Committees of all relevant information about unexpected SAE, suspected to be related to the radiation treatment, that are fatal or life-threatening as soon as possible, and in any case no later than seven days after knowledge of such a case. Relevant follow-up information for these cases will subsequently be submitted within an additional eight days.

Once a year throughout the clinical trial, the sponsor will provide an updated safety report highlighting SAE to the Ethics Committee. For events not reported in the CTCAE version 5.0, the investigator will use the grade or adjectives reported in the following:

Grade 1 Mild does not interfere with patient's usual function

Grade 2 Moderate Interferes to some extent with patient's usual function

Grade 3 Severe, Interferes significantly with patient's usual function

Grade 4 Life-threatening, results in a threat to life or in an incapacitating disability

Grade 5 Death

